5.2 Safety Endpoints

5.2.1 Secondary Safety Endpoint

Incidence of treatment emergent adverse events (TEAEs) related to the Ulthera DeepSEE System, as reported by the treating investigator throughout the trial.

5.2.3 Definitions Related to Safety Endpoints

5.2.3.1 TEAE

Treatment-emergent AEs (TEAEs) are defined as AEs with onset at or after the administration of trial treatment. For subjects randomized to treatment, an AE is considered a TEAE if the start date is on or after treatment at Day 1. For subjects randomized to control, an AE is considered a TEAE if the start date is on or after treatment at Day 90.

5.2.3.2 TESAE

TESAEs are defined as TEAEs which meet any seriousness criterion of SAE.

5.2.3.3 Treatment related TEAE

Treatment related AEs are defined as AEs whose causal relationship are related or missing.

6 Statistical Analysis Methods

Metric statistics will be number of values analyzed (n), number of observed values (n obs), number of imputed values (n imp), mean, standard deviation (SD), median, lower quartile (Q1), upper quartile (Q3), minimum (min), and maximum (max). Mean, quartiles and median will be reported to one decimal place more than the data were collected, for the standard deviation two decimal places more will be displayed; for derived data, the number of decimal places will explicitly be given in the Sections below.

Frequency tables for qualitative endpoints/variables will present absolute and percent frequencies (n, %). Frequency tables will include the number of missing values unless otherwise specified. Percentages will be calculated using the denominator of all subjects in a specified population or treatment group. Percentages will be calculated using the number of subjects with non-missing data at the corresponding visit as denominator (observed cases). The denominator will be specified in a footnote to the tables for clarification if not otherwise obvious. Percentages will be reported to one decimal place.

If not otherwise specified, statistical tests will be conducted two-sided at type I error rate 5%. P-values will be reported to four decimal places (e.g., p=0.0375). P-values below 0.0001 will be presented as '<0.0001'. P-values above 0.9999 will be presented as '>0.9999'. Confidence intervals (CIs) will be two-sided 95% CIs.

All statistical analyses will be performed using SAS

6.1 Effectiveness Endpoints

If not otherwise specified, effectiveness analyses will be based on observed cases in the FAS. For the FAS, all subjects will be analyzed as randomized.

6.1.1 Primary Effectiveness Endpoint

6.1.1.1 Primary analysis

Proportion of subjects with improvement at Day 90 = number of subjects with improvement at Day 90 / number of subjects in the analysis set and group * 100, the result will be rounded to 1 decimal place.

If improvement is considered as event, the null and alternative hypotheses to be tested are:

 H_0 : odds ratio of Treatment vs. Control = 1 (null hypothesis)

versus H_1 : odds ratio of Treatment vs. Control $\neq 1$ (alternative hypothesis).

Effectiveness of treatment is confirmed if
the p-value of the test is \leq 5% and the odds ratio is in favor of Treatment (i.e., $>$ 1).

6.1.1.2 Sensitivity analyses

2 6:4- -66--4-

The following sensitivity analyses will be conducted to support the primary analysis:

- 1. Observed cases: the same approach as outlined for the primary analysis will be applied to observed cases instead of multiple imputation.
- 2. PPS: the observed cases analysis will be applied to the PPS.

٥.	Site	e effects	
		a '	
1	Dane	adomized got: the same approach as outlined for	the primary analysis will be applied to all

4. Randomized set: the same approach as outlined for the primary analysis will be applied to all subjects in the randomized set.

6.1.1.3 Subgroup analyses

No subgroup analysis is planned for primary effectiveness endpoint.

[figure not shown]

6.2 Safety Endpoints

All safety analyses will be performed on the SES. Subjects will be analyzed as treated. Moreover, safety analyses will be based on the pooled randomized groups if not otherwise specified.

Adverse events will be coded according to the Medical Dictionary for Regulatory Activities (MedDRA) version that is in effect at the time the database is closed to allow for analysis by System Organ Class (SOC) and Preferred Term (PT).

Only TEAEs and TESAEs will be summarized. Similarly, only those device deficiencies that are reported to be associated with devices that were used to treat subjects will be summarized.

Frequency tables will give incidence rates by treatment group and overall.

Calculation of time to onset/duration of AEs (days):

- Time to onset of an AE is defined as start date of AE date of administration of treatment [+ 1 day for TEAEs]
- The duration will be calculated as stop date onset date + 1 day for AEs.

In case of missing intensity or missing causal relationship of an AE the worst case principle will be applied, i.e., a missing intensity will be set to "severe" and a missing causal relationship will be set to "related". Missing outcome will be set to "unknown".

Absolute values and changes from baseline of vital signs will be analyzed by metric statistics, treatment and visit.

[figure not shown]
6.2.1 Secondary Safety Endpoints

Incidence rates of treatment related TEAEs will be provided by PT:

- Overall for all treated subjects;
- Until 90 days after treatment for all treated subjects;

• Until Day 180 for the Treatment group.

Moreover, incidence rates for treatment related TEAEs will be given by SOC and PT, worst intensity, and worst outcome. TEAEs will be sorted by descending frequencies in SOC and PT in total (overall) column.

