8.2 Discussion of Trial Design, Including the Choice of Control Groups

As detailed in Section 8.1, this is a prospective, multicenter, randomized, evaluator-blind, controlled trial. The trial will be conducted at approximately five sites to improve data homogenization and to minimize site-associated biases. This multicenter design approach will also increase the representativeness of the trial results. Randomization will eliminate selection bias in treatment assignment.

Since no approved, marketed, directly comparable products are currently available in China for treatment of lower face and submental laxity, an untreated Control Group will be used for the primary effectiveness assessment in this trial. To maximize the number of subjects exposed to acquire adequate safety data, subjects in the Control Group will receive delayed treatment with the Ulthera DeepSEE System at Day 90 upon completion of all effectiveness assessments.

The trial duration of 180 days represents a reasonable timeframe to assess effectiveness as well as delayed-onset and/or long-term AEs. A single treatment protocol using three transducers targeting specific tissue depths at a variable energy level was chosen based on published results. Those studies indicate effectiveness for the majority of subjects and capture of any potential AEs at 90 days following treatment.[2, 8, 9] Following the Treatment Group until Day 180 ensures capture of any late responders to treatment as well as potential delayed-onset or long-term AEs.

Ulthera DeepSEE treatment maps used in this trial (Section 10.5.1.3) represent a safe standard for treatment of the lower face and submentum based on the consensus guidelines.[13] As recommended by the consensus guideline, for the majority of individuals, use of the DS 10-1.5 and DS 7-3.0 transducers are appropriate for treatment of the mid-to-deep reticular layer of the dermis and subdermis, whereas the DS 7-3.0 and DS 7-4.5 transducers are utilized to target the deeper facial planes such as the superficial musculoaponeurotic system and platysma, dependent on individual anatomy and the aesthetic subunit being treated. Pre-treatment visualization of the tissue depths in each subject is used to preclude treatment at the level of large neurovascular structures or bone.

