11 TRIAL PROCEDURES

11.1 Visit Schedule

The investigation activities and visit schedule are detailed in the Schedule of Events

The screening visit (V1) is required to determine subject eligibility for trial participation; this visit must be completed -14 to -3 days prior to Day 1 (V2). Eligible subjects will be randomized during the screening period (Day -14 to -3) to either the Treatment Group or Control Group.

At Day 1, the Treatment Group will receive a single treatment with the Ulthera DeepSEE System to the midface, lower face, submentum, and upper neck with three DS transducers (DS 10-1.5, DS 7-3.0, DS 7-4.5). The Control Group will not receive treatment at Day 1, and will remain untreated until Day 90. Following completion of all protocol-mandated assessments at Day 90, the Control Group will receive a single treatment with the Ulthera DeepSEE System to the midface, lower face, submentum and upper neck with three DS transducers (DS 10-1.5, DS 7-3.0, DS 7-4.5).

All treatments should be administered at the investigative site by the primary treating investigator or designated back-up treating investigators, occurring only after completion of all required pre-treatment procedures and assessments.

Following treatment with the Ulthera DeepSEE System, subjects will be observed for a minimum of 30 minutes. Subjects in both trial groups will be contacted by telephone at 3 days (\pm 1 day) and 14 days (\pm 3 days) after treatment and will have an unscheduled visit if necessary due to safety concerns (Section 11.1.2).

Safety follow-up will occur until Day 180 ± 14 days (V4) for both trial groups, corresponding to 180 days post-treatment for the Treatment Group and 90 days post-treatment for the Control Group.

The primary endpoint visit will occur at Day 90 (\pm 7 days) post-treatment, and the EOT visit will occur at Day 180 (\pm 14 days). In the case of a subject's premature discontinuation of the trial, a final assessment (EOT visit) should be performed.

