2.1 Clinical Trial Design

This is a prospective, 180-day, randomized, multicenter, evaluator-blind, controlled trial designed to evaluate the effectiveness and safety of the Ulthera DeepSEE (DS) System improving the appearance of skin laxity of the lower face and submentum. Subjects will be enrolled from participating investigative sites in China. A total of 200 subjects will be randomized 1:1 to either the Treatment Group or Control Group stratified by investigative site.

The Treatment Group will receive a single treatment at Day 1 with the Ulthera DeepSEE System to the midface, lower face, submentum, and upper neck with three DS transducers (DS 10-1.5, DS 7-3.0, and DS 7-4.5) and will be followed for 180 days after treatment.

The Control Group will not receive treatment at Day 1 and will remain untreated until Day 90 (delayed treatment). Following completion of all protocol-mandated assessments at Day 90, the Control Group will receive a single treatment with the Ulthera DeepSEE System to the midface, lower face, submentum and upper neck with three DS transducers (DS 10-1.5, DS 7-3.0, and DS 7-4.5) and will be followed for 90 days after treatment.

For both the Treatment Group and Control Group, the starting energy level (EL) will be EL2 for the DS 10-1.5 transducer, and EL4 for the DS 7-3.0 and DS 7-4.5 transducers.

All subjects will participate in this trial for 180 days and will be evaluated at screening, Day 1, Day 90, and Day 180. Follow-up telephone calls will occur at 3 days and 14 days after treatment. In case of ongoing transient nerve effects 14 days after treatment, trial personnel will conduct

additional follow-up phone calls with the subject every week until 6 weeks after treatment and document the time of resolution.

After a maximum 14-day screening period, the planned trial duration for individual subjects is 180 days (\pm 14 days).

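### The overall PT rate and the related-TEAE tables by SOC/PT, worst intensity and worst outcome mix 180-day and 90-day follow-up; the SAP's matched windows cover only the PT listings

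*SAP*

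**What the plan says.** Protocol 11.1 sets safety follow-up to the Day 180 visit in both groups, "corresponding to 180 days post-treatment for the Treatment Group and 90 days post-treatment for the Control Group". For Controls the TEAE clock starts late; SAP 5.2.3.1 says: "For subjects randomized to control, an AE is considered a TEAE if the start date is on or after treatment at Day 90".

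SAP 6.2 sets the general reporting rule: "Moreover, safety analyses will be based on the pooled randomized groups if not otherwise specified". It adds: "Frequency tables will give incidence rates by treatment group and overall".

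SAP 6.2.1, in line with Protocol 13.4.2.1, plans related TEAEs by PT in three ways: an overall rate in all treated subjects, a rate limited to the first 90 days post-treatment in all treated subjects, and a rate to Day 180 in the Treatment Group only. A separate sentence then extends the reporting: "Moreover, incidence rates for treatment related TEAEs will be given by SOC and PT, worst intensity, and worst outcome". It names no window. The sentence after it orders events by their frequency in the total column, so a pooled column is expected in these tables.

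**The concern.** Under the nominal schedule, a Control subject leaves observation about 90 days after treatment. In a table without a window, that subject still counts in the denominator for events starting later. The total column then understates late-onset events. The Treatment column may also show more events, or more severe ones, only because that group was watched for twice as long.

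Protocol 8.2 justifies the longer follow-up by exactly these events: "Following the Treatment Group until Day 180 ensures capture of any late responders to treatment as well as potential delayed-onset or long-term AEs". The tables without a stated window are the ones that show how severe related events were and how they ended. Related TEAEs are the named secondary safety endpoint.

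**Working it through.** **Inputs from the documents.** SAP 2.1: "A total of 200 subjects will be randomized 1:1 to either the Treatment Group or Control Group stratified by investigative site", so about 100 per group. Treatment is on Day 1 or Day 90. Protocol 11.1 allows ±7 days around the Day 90 visit and ±14 days around the Day 180 visit. The documents give no event rates, so the rates below are assumptions.

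**Follow-up after treatment.** Using nominal study days, Treatment has 180 days and Control has 180 − 90 = 90. This reproduces the figures in Protocol 11.1. With visit windows, Control ranges from (180 − 14) − (90 + 7) = 69 days to (180 + 14) − (90 − 7) = 111 days. Treatment ranges from 166 to 194.

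**Effect on a total column without a window.** Let p be the risk of a first event by 90 days after treatment and q the added risk afterwards, seen only in the Treatment Group. Then

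pooled rate = [nT(p + q) + nC·p] / (nT + nC).

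*(a) Late onset only (p = 0).* Pooled rate ÷ Treatment rate = nT/(nT + nC). With nT = 100:

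| Controls treated | Factor |
|---|---|
| 100 | 100/200 = 0.50 |
| 90 | 100/190 = 0.53 |
| 80 | 100/180 = 0.56 |
| 70 | 100/170 = 0.59 |

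Fewer than 100 Controls are considered because those who leave before the Day 90 treatment are not in the safety set. As an illustration with an assumed count, three late related events are 3/100 = 3.0% (Clopper-Pearson 95% CI 0.6 to 8.5%) in the Treatment Group and 3/200 = 1.5% (0.3 to 4.3%) in the total.

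*(b) Constant hazard, 100 treated per group.* The Treatment 180-day risk is 1 − (1 − p)², and the total is the mean of that and p.

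| p (Control column) | Treatment column | Total | Total ÷ Treatment | Treatment ÷ Control |
|---|---|---|---|---|
| 2% | 3.96% | 2.98% | 0.75 | 1.98 |
| 5% | 9.75% | 7.38% | 0.76 | 1.95 |
| 10% | 19.0% | 14.5% | 0.76 | 1.90 |

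The last column arises with no true difference between the groups.

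*(c) Mostly early onset (p = 30%, q = 2%).* Total = (100 × 0.32 + 100 × 0.30)/200 = 31%, against 32% in the Treatment Group, a factor of 0.97.

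**Effect of the SAP's own windows.** Limited to 90 days, both columns estimate p. The Treatment-only rate to Day 180 estimates p + q on its own denominator. Neither is diluted.

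**Worst outcome.** A 90-day onset limit does not equalise this table. An event starting 60 days after treatment has a nominal 180 − 60 = 120 further days in which to resolve in the Treatment Group, but 90 − 60 = 30 in the Control Group.

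**The case against.** The strongest reply is that the plan already contains the remedy. By PT there is a 90-day rate in all treated subjects and an undiluted Day 180 rate in the Treatment Group. A reader might infer that every pooled related-TEAE table is distorted, or that late events go unreported at their true rate. The documents do not support that: by PT, late events are reported undiluted, and even in the tables without a window the Treatment column is itself undiluted. This part of the reply stands and limits the point to the overall PT rate and the SOC/PT, intensity and outcome tables.

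A reader might also infer that related events in general are halved. They are not: 0.50 applies only to onset after day 90. Protocol 8.2 cites published studies as indicating that AEs are captured by 90 days, so late onset may be a small share.

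Third, silence about windows is not proof of their absence. The layout is left to mock tables that are not in the documents, and some SAP safety text is not visible. This is a fair caution. But the sentence in question is complete, and the windows before it are attached to the PT rates only.

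Finally, both groups receive the same device treatment, no between-group safety test is stated, and SAP 6.4.4 names the primary effectiveness analysis as the only confirmatory one. This also stands and limits the consequence to how descriptive rates are read.

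**Conclusion.** The point holds for a defined set of tables: the overall PT rate and, as written, the related-TEAE tables by SOC/PT, worst intensity and worst outcome. Their group columns compare a nominal 180 days with 90. Their total column shows events with onset after day 90 at about 0.50 of the Treatment Group rate with 100 treated per group, or 0.53 to 0.59 with 90 to 70 Controls treated. Under an assumed constant hazard the factor is about 0.75, and for mostly early events it is close to 1. These figures rest on nominal follow-up, about 100 treated in the Treatment Group and assumed event rates.

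It would go too far to conclude that the trial's safety finding is biased or that a confirmatory result is at risk. The tables are descriptive, and the PT listings already give both a near-matched and an undiluted rate. What remains is a follow-up artefact in the severity and outcome reporting, which can be removed cheaply.

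**What to change.** In SAP 6.2.1:

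- State that the SOC/PT, worst-intensity and worst-outcome tables are produced for the same two windows as the PT listings: the first 90 days post-treatment in both groups, and to Day 180 in the Treatment Group alone with its own denominator.
- Keep the overall rate, since Protocol 13.4.2.1 specifies it and it also retains Control events starting on days 91 to 111. Footnote it, and any other total without a window, as mixing 180-day and 90-day follow-up.
- Footnote the worst-outcome table to say that the time available for resolution still differs between groups.
- Note that visit windows leave Controls with about 69 to 111 days after treatment, so the 90-day matching is approximate.

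The cost is SAP and table-shell wording plus a few more table blocks. It needs no new data and no protocol change.

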6.4 Special Statistical/Analytical Issues

6.4.2 Baseline and Pre-treatment

Baseline is defined for both treatment group and control group as the last observed value or test result before Day 1. Pre-treatment is as same as baseline in treatment group and defined as the last observed value or test result before Day 90 treatment in control group.

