The Treatment Group will be evaluated at Day 1 (treatment), at 3 days and 14 days post-treatment (phone calls for safety only), Day 90, and Day 180. The Control Group will be evaluated at Day 1, Day 90 (delayed treatment after effectiveness assessments), at 3 days and 14 days post-treatment (phone calls for safety only), and Day 180 (90 days post-treatment).

The primary effectiveness endpoint, the proportion of subjects with improvement in lower face and submental laxity (Section 7.2.1.1), will be assessed for both trial groups at Day 90

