10.5.1 Planned Treatment Procedure and Administration

10.5.1.1 Pre-treatment Assessments

All subject-related, pre-treatment activities (Section 11.1) should be completed prior to administration of pre-treatment medications.

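### Does setting baseline as the last value before Day 1 wrongly shut out assessments made on Day 1 ahead of treatment?

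*SAP*

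**What the plan says.** SAP 6.4.2 defines two reference values. For the first: "Baseline is defined for both treatment group and control group as the last observed value or test result before Day 1". The second, the pre-treatment value, equals that baseline in the Treatment Group. In the Control Group it is "defined as the last observed value or test result before Day 90 treatment in control group".

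The surrounding schedule is as follows.

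- SAP 2.1: subjects "will be evaluated at screening, Day 1, Day 90, and Day 180".
- Protocol 11.1: screening falls 3 to 14 days before Day 1. Treatments are given at the site, "occurring only after completion of all required pre-treatment procedures and assessments".
- Protocol 10.5.1.1: "All subject-related, pre-treatment activities (Section 11.1) should be completed prior to administration of pre-treatment medications".
- Protocol 10.5.2: the Control Group's Day 90 assessments are finished before its treatment at the same visit (V3).

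The public text gives no other definition of baseline. The Schedule of Events, which would assign each measure to a visit, is not shown.

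**The concern.** The baseline rule cuts off at a calendar day, while Control's pre-treatment rule cuts off at an event. Day 1 is a scheduled evaluation visit for everyone, and the protocol expects pre-treatment work to be finished before treatment begins. A reader would expect a value recorded that morning to count as baseline, yet the words exclude it. The next sentence of the same section admits a same-day value for Control at Day 90. The label pre-treatment therefore carries two rules.

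If a baseline-referenced measure were collected at both screening and Day 1, literal programming would pass over the later value for the older one. If it were collected only on Day 1, there would be no baseline at all. Change from baseline in FACE-Q is a named secondary endpoint, so the question is not idle. Any comparison of post-treatment change between the groups would also start from differently timed references.

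**Working it through.** The documents give no figure to reproduce here. The check is date arithmetic, followed by a look at which analyses use the definition.

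**Inputs**

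- Screening: 3 to 14 days before Day 1 (Protocol 11.1).
- Treatment Group treated on Day 1; Control treated at V3 after that visit's assessments (Protocol 10.5.2).
- Primary endpoint visit: 90 ± 7 days after treatment (Protocol 11.1).

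**Age of the reference value at treatment**

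- Treatment Group, literal rule: 3 to 14 days.
- Treatment Group, if a Day 1 value were allowed: 0 days.
- Control pre-treatment value: 0 days possible, because assessment and treatment share a visit.

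**Interval from reference value to the Day 90 visit**

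- Day 1 value: 90 − 7 = 83 to 90 + 7 = 97 days.
- Screening value: 83 + 3 = 86 to 97 + 14 = 111 days.
- For a visit exactly on time: 90 days against 93 to 104 days, so 3/90 = 3.3% to 14/90 = 15.6% longer.

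All the added days fall before treatment. Time from treatment to assessment is unchanged, so the older reference adds only whatever an untreated subject's score varies over 3 to 14 days.

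**Where the definition is used, as far as the text shows**

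| Measure | Visible timing of baseline | Analysis | Effect of the rule |
|---|---|---|---|
| Vital signs | Screening (Protocol 11.2.3.2: V1 and V4 only) | Change from baseline (SAP 6.2) | None |
| FACE-Q | Not shown | Descriptive with confidence interval, Treatment Group only (SAP 6.1.2) | None if taken at screening only; reference 3 to 14 days older if taken at both visits; blank for all if taken on Day 1 only |
| iGAIS, sGAIS | The endpoint is a rating of improvement at Day 90 | Proportion, Treatment Group only (SAP 6.1.2) | No baseline value is subtracted in the visible text |
| Laxity improvement, skin displacement | Not shown | Treatment against Control at Day 90 (Protocol 13.4.1.1, 13.4.1.2) | Same rule in both groups |

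**Between-group bias.** Baseline follows one rule for both groups, and neither group has been treated at that point. Whatever visit supplies it, the randomised Day 90 contrast compares like with like. The two-rule problem affects only the pre-treatment value, and no visible analysis compares change from pre-treatment between the groups.

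**The no-baseline case.** This needs a measure collected on Day 1 and not at screening. The text identifies none. If one exists, the derivation would return an empty baseline for every subject, which cannot pass unnoticed. SAP section 1 provides for quality control of the analysis datasets.

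**The case for a change.** The strongest argument for amending the SAP has four parts.

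- Day 1 is more than a treatment slot. Eligibility is checked again there (Protocol 9.2.1, 9.2.2), and assessments are required before treatment.
- The SAP can anchor to treatment when it wants to. Its definition of a treatment-emergent event (SAP 5.2.3.1) counts from treatment, so the calendar-day wording looks accidental.
- The SAP says it exists to guide programming precisely, and a programmer who quietly uses a Day 1 value departs from it without record.
- The repair is one sentence and one derivation, harmless if every baseline comes from screening and useful if any does not.

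The inconsistency in wording stands, and so does the literal exclusion of Day 1 values. The consequence does not. The only Day 1 check that the visible text spells out is repeat eligibility; the passages on evaluation and pre-treatment activities name no measure.

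There are also sensible reasons for the present form. Control receives nothing on Day 1, so a cut-off at treatment would not define a common baseline, whereas a day does. Subjects learn their assignment at Visit 2 (Protocol 9.2.4), so a screening value is the safer reference for a self-reported score, because it precedes that knowledge. The documents do not give this as the reason, but it means the Day 1 value cannot simply be called the correct one.

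**Conclusion.** No change to the plan is called for. SAP 6.4.2 is loosely drafted, and analysts with the Schedule of Events in hand will fill the gap sensibly, taking baseline from the visit at which each measure is scheduled before treatment.

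The largest effect on an endpoint that can be named is a FACE-Q reference 3 to 14 days older, in a secondary endpoint summarised descriptively for one group. SAP 6.4.4 reserves confirmatory status for the primary endpoint. No bias between groups at Day 90 follows from a rule that both groups share.

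This rests on two assumptions. First, no redacted analysis compares change from pre-treatment between groups; if one does, the Treatment Group's reference would be 3 to 14 days old against possibly 0 for Control. Second, any measure taken solely on Day 1 would be caught when the datasets are built. If all baselines come from screening, as vital signs do, the wording has no effect at all.
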